All IPL treatments will be performed by the same investigator, the PI, who will not be masked. Each subject's eyes will be randomized with one eye/side of the face receiving IPL treatment (Figure 3), and the fellow eye serving as a control. At the first IPL treatment, the energy level (range of 8-18 joules) will be individually determined based the patient's skin Fitzpatrick scale phototype. The IPL instrument, Quadra Q4®, includes four pulse levels (1-4) each with six sublevels (A-F). The pulse intensity is inversely related to the skin phototype scale, and as noted in subject inclusion and exclusion criteria above, we will only treat patients who are phototype 1 through 4. The sublevel D is used for the initial treatment unless the patient cannot tolerate it and then a lower sublevel will be used. Future treatments sublevels will be increased gradually unless the examiner determines this is unsafe for the patient.

The Lumenis M22 IPL device requires the user to input fluence (joules/cm²) level prior to treatment. The below graph shows the fluence levels of the Dermamed Quadra Q4® that correlate to the fluence levels of the Lumenis M22.

		Fitzpatrick Skin type		
	1	2	3	4
A	10J/cm ²	9J/cm ²	8J/cm ²	8J/cm ²
B	11J/cm ²	10J/cm ²	9J/cm ²	8.5J/cm ²
C	12J/cm ²	11J/cm ²	9.5J/cm ²	9J/cm ²
D	13J/cm ²	12J/cm ²	10J/cm ²	9.5J/cm ²
E	14J/cm ²	13J/cm ²	10.5J/cm ²	10J/cm ²
F	15J/cm ²	14J/cm ²	11J/cm ²	10.5J/cm ²

Figure 3. IPL treatment. After placing eye shields, an ultrasound gel is applied. Treatment spots are done around the eye, lower eyelid, cheek, side of nose and temple.

b. Sham Treatment

With the eye shields still in place, the fellow eye will be treated with approximately 15 spots of pressure around the eye, lower eyelid, cheek, side of nose and temple with the IPL device. No light energy will be applied. The PI will only place the device on the participant and press to mimic actual IPL treatment. Ultrasound gel will be applied to these areas prior to the sham treatment to prevent unmasking of the participant.

c. Post-Treatment

After the IPL and sham treatments have been completed, the eye shields will be removed, and the face cleaned. The upper and lower lids of both eyes will be expressed with a meibomian gland expressor while being positioned at the slit lamp.

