After treatment, as recommended by the manufacturer, each subject will be asked to use ketorolac twice a day for three days and to wear SPF 30 sunscreen for one week. During the course of the treatment period, any adverse events will be noted per the adverse reporting guidelines outlined in section D.

d. 1 Week Safety Follow Up Phone Call (+/- 2 days)

Approximately one week after the participants have completed the baseline visit and received the IPL and sham treatments, a member of the study team will contact the participants to answer any questions and to document any adverse events.

e. Follow Up Visits (+/- 10 days)

Participants will return to the clinic for 4 additional visits after the baseline visit (visit 1).

At visits 2, 3, and 4, participants will be evaluated by a corneal specialist who is masked to the IPL treatment randomization, complete the testing outlined in the schedule of events (appendix A), and receive IPL and sham treatments accordingly. Participants will receive a total of 4 IPL and sham treatments throughout the duration of the study.

Participants will be asked to return to the clinic approximately 16.5 weeks after their baseline visit to complete visit 5. They will complete the testing outlined in the schedule of events but will not receive IPL or sham treatments.

f. 7 Month Follow Up Phone Call (+/- 5 days)

After the participant's final visit (visit 5) a member of the study team will contact the participant approximately 7 months after their baseline visit. Participants will be asked to complete the OSDI and NEI-VFQ questionnaires over the phone. After completion of the questionnaires, the study team member will inform the participant of which eye received the IPL treatment and which eye received the sham treatment. Also during this call, the participants will be offered to complete an optional visit. At this optional visit they will be asked to complete the testing outlined in the schedule of events and will be offered IPL treatment on both eyes free of charge. Patient's that do not wish to come in for the optional visit and IPL treatments, end their participation after completing the questionnaires, if they did not choose to end it sooner.

D. Reporting Procedures

i. Adverse Events

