- a.** Adverse events (AEs) and complications determined by the investigator to be "possibly", "probably" or "definitely" related to the IPL treatment or study procedures will be recorded and reported to the IRB according to their reporting guidelines.
- b.** Any AE that is determined by the investigator to meet the definition of an unanticipated problem involving risks to subjects or others will be reported within 7 days to the IRB if is determined to be a serious problem. If the unanticipated problem is determined to be non-serious, it will be reported to the IRB within 14 days.

ii. Serious Adverse Events

- a.** Any AE which meets the FDA definition of serious and determined by the investigator to be "possibly", "probably" or "definitely" related to the IPL treatment or study procedures will be recorded and reported to the IRB within 7 days.

iii. Other Reportable Occurrences

- a.** All protocol deviations will be reported to the IRB at the continuing renewal.
- b.** Any privacy violation or breach of confidentiality will be reported to the IRB within 7 days and within 24 hours to the UMHS Privacy Office.

iv. Unmasking

- a.** Unmasking of the participant will occur after completion of the ODSDI and NEI-VFQ questionnaires during the 7 month follow up call.
- b.** Unmasking may occur at any time point throughout the trial if it is determined by an investigator to be in the best interest of the participant.

E. Statistical Methods

i. Sample Size and Power

The primary study outcome (pre to post change in TBUT within the treated eye and also the untreated, control eye) dictated the use of a paired statistical approach to sample size estimation. Based on our preliminary data, other published dry eye studies[17], and recent meeting abstract (ASCRS 2014; Gupta PK et al.) the expected, clinically relevant pre to post TBUT increase of 3 seconds with a standard deviation of 4.5 seconds was used. Type I and II error estimates used were standard for a non-pivotal study, 0.05 & 0.20. The estimated the sample size needed detect this difference in TBUT is 27 subjects. We will recruit 30 subjects allowing for an anticipated 10% drop-out rate.

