Appendix A: Schedule of Events

Procedure	Baseline (Visit 1)	1 week phone call (+/- 2 days)	Visit 2, 4.5 weeks (+/- 10 days)	Visit 3, 8.5 weeks (+/- 10 days)	Visit 4, 12.5 weeks (+/- 10 days)	Visit 5, 16.5 weeks (+/- 10 days)	7 month phone call (+/- 5 days)	Optional Visit (e)
Informed Consent (a)	X							
Pregnancy Test (a)	X							
Review of Systems (a)	X		X	X	X	X		
Ocular and Systemic Medications (a)	X		X	X	X	X		
Adverse Event Assessment (a)		X	X	X	X	X		
Pinholed ETDRS Visual Acuity (a)	X		X	X	X	X		X(f)
OSDI Questionnaire (a)	X		X	X	X	X	X	
NEI-VFQ Questionnaire (a)	X		X	X	X	X	X	
Tear Osmolarity (a)	X						X	
Eyelid Photography at Slit Lamp (a)	X						X	
Facial Photography (a)	X						X	
Meibography (a,c)	X						X	
TBUT (b)	X		X	X	X	X		X
Fluorescein Staining (b)	X		X	X	X	X		X
Lissamine Green Staining (b)	X		X	X	X	X		
Meibomian Gland Evaluation (b)	X		X	X	X	X		

Schirmers Test (c)	X		X	X	X	X		
Intraocular Pressure Measurement (c)	X		X	X	X	X		
Randomization (c)	X							
Unmasking (d)							X	
IPL and Sham Treatment (c)	X		X	X	X			X (IPL to both eyes)
Expression of Upper and Lower Lids (c)	X		X	X	X			X
Begin ketorolac Instillation (twice a day for three days) (c)	X		X	X	X			X

** All tests are completed on both eyes except that IPL treatment is performed on one eye and the sham treatment is performed on the other.

** Fluorescein staining, lissamine green staining and Meibomian gland evaluation are to be completed right eye and then left eye.

- a- Indicates that it is to be completed by study coordinator/technician (excludes the optional visit).
- b- Indicates that it is to be completed by a masked corneal specialist (excludes the optional visit).
- c- Indicates that it is to be completed by the unmasked PI.
- d- Unmasking of the participant will occur after completion of the ODSDI and NEI-VFQ questionnaires.
Unmasking may occur at any time point throughout the trial if it is determined by an investigator to be in the best interest of the participant.
- e- Can be completed entirely by Unmasked PI
- f- ETDRS visual acuity testing may be substituted for standard Snellen visual acuity at optional visit

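### Section D requires an adverse event to be recorded only if it is judged related to treatment or study procedures, which conflicts with the 1-week call and leaves events judged unrelated without a required record

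*Combined protocol and SAP*

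**What the plan says.** Four parts of the protocol bear on which AEs are written down.

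- **Section D.i.a (Adverse Events).** AEs that the investigator judges possibly, probably or definitely "related to the IPL treatment or study procedures will be recorded and reported to the IRB according to their reporting guidelines". One condition governs both recording and reporting.
- **Section D.ii.a (Serious Adverse Events).** The rule covers "Any AE which meets the FDA definition of serious and determined by the investigator to be" at least possibly related. Again the condition applies to recording as well as to IRB reporting.
- **Section C.iii.c (Post-Treatment).** During the treatment period, "any adverse events will be noted per the adverse reporting guidelines outlined in section D".
- **Section C.iii.d (1-week call).** Here "a member of the study team will contact the participants to answer any questions and to document any adverse events", with no relatedness condition.

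Appendix A lists an AE assessment at the 1-week call and at visits 2, 3, 4 and 5 and assigns it to the coordinator or technician. It does not say which events are to be recorded. On masking, section C.iii.a states: "All IPL treatments will be performed by the same investigator, the PI, who will not be masked". Section D refers only to the investigator.

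**The concern.** Recording an event and reporting it to the IRB serve different purposes. A causality threshold is an ordinary filter for reporting. As a filter for recording, it puts a judgement about a single case ahead of the data. An event wrongly called unrelated is then not there to be re-assessed, and a pattern across participants cannot emerge.

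The paired design adds a second issue. Both eyes have their lids expressed and only one side receives light, so the sham side is the natural reference for telling IPL effects from expression and background effects. That reference is useful only if events on both sides pass through the same filter. An assessor of relatedness who knows the treated side could apply a different threshold to each side, and the plan neither names the assessor nor requires masking.

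**Working it through.** The plan states no figure on this point, so the check is mainly textual.

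**1. Same event, different contacts.** Take an AE that the investigator judges unrelated.

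- Reported at the 1-week call: C.iii.d says to document it. C.iii.c, read with D.i.a, contains no requirement to record it. The two conflict.
- Reported at visit 2, 3 or 4: Appendix A calls for an assessment. The only rule on what to record is C.iii.c, which points to D.i.a. No record is required.
- Reported at visit 5: the treatment period is not defined. If it has ended, section D is still the only text on what is recorded.
- Serious: D.ii.a applies the same condition. No record is required.

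**2. How far the unfiltered contact reaches.** Treatments are given at baseline and at visits 2, 3 and 4, four in all. The 1-week call follows only the first. After treatments 2, 3 and 4 the next scheduled contact is the following visit, about 4 weeks later (8.5 − 4.5, 12.5 − 8.5 and 16.5 − 12.5 weeks). So the one contact expressly worded to document any AE follows 1 of 4 treatments.

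**3. Other routes to a record.** D.i.b covers "Any AE that is determined by the investigator to meet the definition of an unanticipated problem involving risks to subjects or others". It has no express relatedness condition, but it is an IRB-reporting rule that also depends on an investigator's determination. It does not require ordinary unrelated AEs to be recorded.

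**4. What the filter could do to a comparison of sides (illustration only).** Let p be the true AE rate, equal on both sides. Let q(IPL) and q(sham) be the probabilities that an event on each side is judged related and so recorded. These are assumptions; the documents give none.

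Recorded rate on a side = p × q for that side. Apparent ratio = [p × q(IPL)] / [p × q(sham)] = q(IPL) / q(sham), which does not depend on p.

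| q(IPL) | q(sham) | Apparent ratio |
|---|---|---|
| equal | equal | 1.0 |
| 0.90 | 0.50 | 0.90/0.50 = 1.8 |
| 0.90 | 0.25 | 0.90/0.25 = 3.6 |
| 0.50 | 0.90 | 0.50/0.90 = 0.56 |

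The absolute difference does depend on p. With 0.90 against 0.50 it is 0.05 × 0.40 = 2.0 percentage points at an assumed p of 5%, and 0.25 × 0.40 = 10.0 points at 25%.

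The side of an event is a further gap. No text requires it to be recorded, and section E describes no tabulation or comparison of AEs by side.

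**The case against.** The strongest reply is that section D is headed as reporting procedures and is about what goes to the IRB. C.iii.c speaks of any AEs being noted, and assessments are scheduled at five contacts. On that reading all events are captured and only related ones are sent on. This may well be the intention, but the text does not secure it: recording itself is made conditional, and the sentence about noting AEs points back to that condition. What stands is that the plan is inconsistent rather than uniformly restrictive.

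A reader might infer three stronger things that the documents do not support.

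- **That only related events are ever recorded.** The 1-week call says otherwise, the visit assessments state no filter, and unanticipated problems have their own rule.
- **That the unmasked treating investigator does the filtering.** This is possible, but section D does not identify who judges. The assessment is assigned to a coordinator or technician whose masking is not stated.
- **That the two sides cannot be compared fairly.** Events related to study procedures, which would include the sham application and lid expression, remain recordable, so sham-side events are not excluded by rule. Bias needs a judgement that differs by side. No stated goal or planned analysis depends on such a comparison.

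Nor should the loss be scaled by the 14% AE rate that section B.ii quotes from a retrospective series. Those events were mostly mild, transient swelling around the eye, which would probably be judged at least possibly related and pass the filter. The documents give no rate for events wrongly called unrelated.

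**Conclusion.** The point holds as a defect in the recording rule. Followed as written, sections C.iii.c and D leave AEs and serious AEs judged unrelated without a required record, most clearly after treatments 2 to 4, and they contradict the 1-week call. The number of events affected cannot be computed from the documents.

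Bias between sides is conditional. It arises only if relatedness is judged differently on the two sides, and its direction is unknown. The ratios from 0.56 to 3.6 rest entirely on assumed recording probabilities and equal true rates; they show sensitivity and are not an estimate. The efficacy and quality-of-life analyses are unaffected. The change is still worth making, because an event that was never recorded cannot be recovered at analysis.

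**What to change.** - Reword D.i.a and D.ii.a so that all AEs and serious AEs are recorded whatever the judged cause, with side (IPL, sham, both, systemic), onset and severity.
- Keep the possibly, probably or definitely related condition, and apply it to IRB reporting only.
- Reconcile C.iii.c, C.iii.d and Appendix A with that rule, so that the 1-week call and visits 2 to 5 all record on the same basis.
- State who judges relatedness and whether that person is masked to side, with masking where possible.
- Add to section E a descriptive tabulation of AEs by side.

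The cost is an amendment to the wording, a few more case report form lines at contacts already scheduled, and one descriptive table. No extra visit or participant is needed, and the IRB-reporting thresholds stay as they are.

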All three study goals have a paired design wherein the first two goals contrast pre- to post-treatment measures in the treated eye, and the 3rd compares the treated eye to the control eye. The primary analysis for each objective will apply the paired, Student's t-test to contrast the continuous outcome variables for efficacy assessment (TBUT, Shirmer's test, corneal staining) in the treated eye (Goal 1) and the patient's quality of life (Goal 2), and the treated vs. control eye measures (Goal 3) from pre-treatment to post-4th treatment times. If the parametric assumptions of this test are not met, the non-parametric equivalent test, the Wilcoxon signed rank test, will be applied. In all cases, the null hypothesis to be tested is one of no change from pre- to post treatment, with a Type I error probability of 0.05 for the primary outcome assessment. The pattern of change over the 4 treatment visits in these continuous variables will be assessed using mixed, linear regression. SAS version 9.4 statistical software (SAS Institute, Cary, NC) will be used.

F. Summary and Long-Term Plan

Dry eye disease is a prevalent ocular condition with inadequate treatments available for proper relief. IPL has the potential to help those with evaporative dry eye due to meibomian gland dysfunction. This is a new treatment that needs to be studied with more rigor to understand the magnitude of the benefit for the relief of symptoms and reduced clinical signs. This study will provide answers to these questions in a prospective, masked design with the hope of providing an improved quality of life to those with DED.

We plan to use the anticipated results from this pilot study to apply for funding for a larger, prospective study on a specific population at high risk for severe DED, those with graft versus host disease. These patients often have extreme dry eye due to damage to the lacrimal and meibomian glands. Kellogg Eye Center has a large volume of these patients from the University of Michigan Cancer Center. Often the current dry eye treatments are not sufficient to effectively treat their DED. There are currently no studies on the efficacy of IPL on this population. This project would require additional funding through another grant. With addition funding, we also

hope to purchase a meibographer to image the entire meibomian glands in the tarsal plate to detect atrophic glands which are unlikely to respond to treatment.

G. References:

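### The stated 27 subjects do not follow from the stated inputs: a paired t-test with a 4.5 s SD of change needs 20, and 27 gives about 92% power rather than 80%

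*Combined protocol and SAP*

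**What the plan says.** Section E.i (Sample Size and Power) names the primary outcome as the "pre to post change in TBUT within the treated eye and also the untreated, control eye" and says that this led to a paired calculation. The inputs are a "pre to post TBUT increase of 3 seconds with a standard deviation of 4.5 seconds was used", and "Type I and II error estimates used were standard for a non-pivotal study, 0.05" for type I, with 0.20 for type II. The result is: "The estimated the sample size needed detect this difference in TBUT is 27 subjects". The last step is "We will recruit 30 subjects allowing for an anticipated 10% drop-out rate".

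The analysis text that follows in Section E names the test: "The primary analysis for each objective will apply the paired" Student's t-test, with the Wilcoxon signed rank test if its assumptions fail. It says that "the null hypothesis to be tested is one of no change from pre- to post treatment". The error rate is repeated there: "with a Type I error probability of 0.05 for the primary outcome assessment". Neither paragraph states the sidedness, a pre/post correlation, a formula, a non-parametric inflation or a multiplicity adjustment to the sample size.

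**The concern.** The section gives an effect, an SD, two error rates and a paired test. If the SD is that of the change, these fix the sample size once sidedness is chosen, and 27 is well above what they imply. So the stated n, SD and type II error cannot all hold on that reading.

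The practical issue is which SD of change the trial was sized on. If it was 4.5 s, 27 evaluable subjects give about 92% power for 3 s. If it was about 5.3 s, they give about 80%. A reader cannot tell which. The uncertainty also carries over to the randomised comparison of treated and control eye (the third goal): any detectable difference in seconds derived from this SD is about 18% larger with 5.3 s than with 4.5 s (5.3/4.5 = 1.18). Section F calls this a pilot for a larger study, so an SD that cannot be reconstructed could be carried forward.

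**Working it through.** **Inputs (Section E).** Mean change 3 s; SD 4.5 s; type I error 0.05; type II error 0.20; paired t-test; 10% dropout. Two-sided testing is assumed, because the null is one of no change; one-sided results are also shown.

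**Attempt to reproduce 27, with 4.5 s as the SD of the change.** The standardised effect is 3/4.5 = 0.667.

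- Normal approximation, two-sided: n = ((1.960 + 0.842) × 4.5/3)² = 17.66, so 18.
- Exact paired t-test: power comes from the noncentral t distribution with n − 1 degrees of freedom and noncentrality 0.667√n.

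| Test | n | Power |
|---|---|---|
| Two-sided | 19 | 0.785 |
| Two-sided | **20** | **0.807** |
| Two-sided | 27 | 0.915 |
| Two-sided | 30 | 0.942 |
| One-sided | 15 | 0.791 |
| One-sided | 16 | 0.816 |

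The stated inputs therefore give 20 two-sided or 16 one-sided. At 27 the type II error is 1 − 0.915 = 0.085, and 80% power is reached at 2.52 s rather than 3 s.

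**What would give 27?**

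- *A larger SD of change.* Two-sided at 80% power, n is exactly 27 when the SD of change lies between 5.247 and 5.356 s. With 5.3 s, 27 subjects give 80.8%.
- *4.5 s as a single-visit SD.* Assuming equal SDs before and after treatment, SD of change = 4.5 × √(2(1 − ρ)), where ρ is the pre/post correlation:

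| ρ | SD of change (s) | n, two-sided | Power at 27 |
|---|---|---|---|
| 0 | 6.36 | 38 | 0.655 |
| 0.2 | 5.69 | 31 | 0.751 |
| 0.30 | 5.32 | 27 | 0.805 |
| 0.32 | 5.25 | 27 | 0.816 |
| 0.4 | 4.93 | 24 | 0.861 |
| 0.5 | 4.50 | 20 | 0.915 |
| 0.6 | 4.02 | 17 | 0.961 |

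  So 27 needs ρ of about 0.30 to 0.32 (about 0.25 by the normal approximation). One-sided, it needs 0.09 to 0.11. No correlation is given.
- *A smaller alpha.* Two-sided 0.05/3 gives 27 (power 0.810; 26 gives 0.791) and 0.05/2 gives 24. Section E states 0.05 twice.
- *Higher power.* 90% gives 26 and contradicts the stated 0.20.
- *Wilcoxon fallback.* 20/0.955 gives 21; the worst-case efficiency, 20/0.864, gives 24.

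**Dropout.** 27/0.9 = 30, as stated. From 20 it would be 20/0.9 = 22.2, so 23.

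**Treated versus control eye (illustration only; the plan claims no power for it).** With 27 pairs, 80% power is reached at 0.560 times the SD of the between-eye difference in change. The expected 95% confidence interval half-width is t(0.975, 26)/√27 = 0.396 times that SD. If both eyes have the same SD of change s and the between-eye correlation is r, the SD of the difference is s√(2(1 − r)):

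| r | Detectable (s), s = 4.5 | Detectable (s), s = 5.3 | Half-width (s), s = 4.5 | Half-width (s), s = 5.3 |
|---|---|---|---|---|
| 0 | 3.56 | 4.20 | 2.52 | 2.97 |
| 0.25 | 3.09 | 3.64 | 2.18 | 2.57 |
| 0.5 | 2.52 | 2.97 | 1.78 | 2.10 |
| 0.75 | 1.78 | 2.10 | 1.26 | 1.48 |

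**The case against.** The best defence is that this is incomplete reporting rather than a proven miscalculation. The text never says outright whether 4.5 s describes the change or a single visit, and the preliminary data, published studies and meeting abstract behind it may hold the missing input. On the natural reading the trial exceeds its stated power, it describes itself as a non-pivotal pilot, and no enrolment figure or decision rule changes. The correlation table also needs equal SDs at the two visits, and the between-eye figures need assumptions that the plan does not supply.

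Much of this is fair. Which input produced 27 cannot be settled from the document, and the two illustrative tables are conditional on their assumptions. But the sentence attaches the 4.5 s to the pre-to-post increase, and on that reading the stated n and type II error disagree; that is more than a missing detail. Section B.i also makes the single-visit reading less plausible: mean TBUT was 1.05 s at baseline and 5 s after three treatments, and an SD of 4.5 s around a baseline mean of 1.05 s is hard to credit for a time that cannot be negative. That supports the reading that gives 20. The conservative direction limits the consequence but does not reconcile the figures.

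**Conclusion.** The concern holds. With 4.5 s as the SD of the change, the stated inputs require 20 evaluable subjects two-sided. The stated 27 is 7 more (30 enrolled against 23 after 10% dropout) and has 91.5% power. Two-sidedness is an assumption, but one-sided testing moves the answer further from 27, to 16. Every route found to 27 adds an unstated input or overrides a stated one.

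On this reading the within-eye test is not underpowered. Two-sided power at 27 would fall below 80% only if 4.5 s were a single-visit SD with equal SDs at both visits and a pre/post correlation below about 0.29. No shortfall is claimed for the treated-versus-control comparison, which Section E.i does not size. The paragraph should be corrected, but the error is not fatal to the trial.

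**What to change.** Keep 30 enrolled and restate the calculation in one of two ways.

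- **(A) If 4.5 s is the SD of the change:** *With 27 evaluable subjects, a paired t-test at two-sided alpha 0.05 has about 92% power for a 3 s within-eye change in TBUT, taking the SD of the change as 4.5 s; 20 subjects would give 80%.*
- **(B) If another input produced 27:** state it, with the sidedness. That means either what the SD refers to and the pre/post correlation (for example a single-visit SD of 4.5 s with correlation 0.30, hence an SD of change of 5.3 s), or the alpha actually used.

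As a secondary addition: *This calculation concerns the within-eye change only. For the treated-versus-control difference in change, 27 pairs give 80% power for 0.56 times its SD.* Convert that to seconds only with the SD confirmed under (A) or (B) and a declared between-eye correlation, and report that comparison with its estimate and 95% confidence interval.

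The cost is one reworded paragraph, with no change to enrolment, visits or tests. The authors must go back to the original calculation. If it cannot be recovered, (A) remains accurate, but it reports the power of a fixed n and does not explain how 27 was chosen.
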